6.2 Duration of Therapy and Patient Withdrawal Criteria

In the absence of toxicity or unacceptable adverse events, it is expected that patients will remain on study treatment for 104 weeks. Patients will receive study drug unless they have unacceptable toxicity, withdraw informed consent, or are withdrawn from the study.

Reasons for withdrawal of study therapy regardless of length of time on study include the following:

- Unacceptable toxicity, defined as:
 - Occurrence of an AE that is related to treatment with the study drug which, compromises the patient's ability to continue; or
 - o Persistent AE requiring a delay of therapy for more than 4 weeks (28 days).
- Intercurrent illness that requires a delay of therapy for more than 4 weeks (28 days).

Protocol Version 4, 06 OCT 2021

Confidential

Page 24 of 70

- Patient chooses to withdraw from the study.
- Patient becomes pregnant.
- Patient noncompliance.
- Any other reason, in the opinion of the Investigator, that renders the patient no longer appropriate for study continuation.

Patients will be advised that they are free to withdraw from the study at any time for any reason or, if necessary, the Investigator, or medically qualified delegate, may discontinue a patient from the study to protect the patient's health.

The date and reasons for withdrawal/discontinuation will be recorded in the electronic case report form (eCRF) and included in the final clinical study report, along with any AEs and necessary medical treatment.

In the event that a patient is discontinued from the study due to an SAE, the Investigator, or medically qualified delegate, will evaluate the urgency of the event. If the situation warrants, the Investigator, or medically qualified delegate, will take appropriate diagnostic and therapeutic measures and make attempts to notify the Sponsor MM. If the situation is not an immediate emergency, the Investigator, or medically qualified delegate, at the clinical study facility will attempt to contact the Sponsor MM for consultation. No medical help, diagnosis, or advice will be withheld from the patient due to an inability to contact the Investigator or medically qualified delegate. The patient will be encouraged to remain available for follow-up medical monitoring. The Sponsor will be notified as soon as possible of any patient withdrawals.

If a participant withdraws consent to participate in this research project, they are entitled to request that all previously retained identifiable biological samples are destroyed, to prevent further analysis according to national provisions.

6.3 Duration of Follow-up

Patients removed from study for unacceptable AE(s) will be followed until resolution or stabilization of the AE(s). Otherwise, patients will have a final follow-up visit approximately 4 weeks after the last dose of study therapy.

6.4 Suspension or Termination of Study at the Investigational Site

The Sponsor reserves the right to terminate the investigational site or this study at any time. Reasons for termination may include, but are not limited to, the following:

- Unacceptable safety and tolerability of study drug.
- The incidence or severity of AEs or SAEs that are observed in this study indicates a potential health hazard to patients.
- Serious or persistent non-compliance by the Investigator with the protocol, Clinical Trial Research Agreement, principles of the ICH Good Clinical Practice (GCP), or applicable regulatory guidelines in conducting the study.
- Human Research Ethics Committee decision to terminate or suspend approval of the Investigator.
- Investigator request to withdraw from participation.
- Patient enrolment rate is unsatisfactory.

6.5 Duration of the Study

Protocol Version 4, 06 OCT 2021

Confidential

Page 25 of 70

The primary study analysis will occur when target enrolment is complete, and each patient either completes 104 weeks on study, or withdraws. Patients may continue to receive study medication unless evidence of unacceptable toxicities as outlined in Section 6.3.

If a patient is noted to still have ongoing toxicities at the End of Study (EoS) visit, they will be followed until resolution or stabilization of the AE(s).

6.6 Trial stopping criteria

The trial will be discontinued if one or more of these criteria are indicated:

- Substantial deviations from the approved protocol
- Adverse-effects of unexpected type, severity, or frequency are encountered
- As the trial progresses, the continuation of the trial would disadvantage some of the participants as determined by the CI team/researchers, trial monitors or the DSMB.

6.7 Dose Stopping Rules and Individual Dosage Adjustments

Dosing may be stopped or modified if suspected adverse drug reactions, changes in vital signs, ECGs, or clinical laboratory results are observed, and these changes pose a significant health risk. Of particular note for dose discontinuation are the following criteria;

- Corrected QT/QTc interval is in excess of 500 ms, or if it increases > 50 ms compared to baseline (baseline will be calculated as the mean of two time points, screening and baseline day 1).
- Occurrence of QT/QTc interval prolongation in association with symptoms of arrhythmia
- Subsequent prescription of a drug with potential QTc prolongation (Antimalarial; Macrolides; Quinolones; Triazole antifungals; Anti-arrhythmic; Antiemetic; Antidepressant; Antipsychotics)
- Evidence of Liver dysfunction, or primary biliary cirrhosis
- If for any reason the Investigator determines that continued participation in the trial is not in the participant's best interest.

The study may be terminated at any point in time at the discretion of the Sponsor.

Clinically or medically significant suspected adverse drug reactions, and SAEs considered to be related to study procedures will be followed until resolved or considered stable.

If an unscheduled interruption of treatment occurs, the PI should notify the Sponsor (via the Clinical Research Organization [CRO]) at the earliest possible time. A missed dose will not be made up. In the event that a patient requires an unscheduled interruption of treatment under conditions other than those associated with toxicity, the case will be reviewed by the PI and the MM, and discussed with the Sponsor/CRO to determine whether such a patient will be allowed to resume treatment.

At the discretion of the Investigator, a participant may be reinstated in the study 4 weeks after discontinuation of the participant. This will be evaluated on a case by case basis, and will also be reviewed by the DSMB. Participants will have a safety evaluation 4 weeks following study drug discontinuation.

6.8 Participant Withdrawal

Protocol Version 4, 06 OCT 2021

Confidential

Page 26 of 70

If a participant decides to withdraw from the project, participants are asked to notify a member of the research team. This notice will allow that person or the research supervisor to discuss any health risks or special requirements linked to withdrawing with the participant. Participants will be made aware that the decision to withdraw from the study will not affect their future treatment or relationship with the study doctor.

If a participant withdraws consent during the research project, the study doctor and relevant project team members will not collect additional personal information from the participant. However, personal information already collected will be retained to ensure that the results of the research project can be measured properly and to comply with law. Participants will be made aware that data collected by the Sponsor up to the time the participant withdraws will form part of the research project results. If a participant decides to leave the research project, they will be encouraged to:

- Tell the study doctor
- Return to the study doctor for one more visit

If a participant withdraws consent to participate in this research project, they are entitled to request that all previously retained identifiable biological samples are destroyed, to prevent further analysis according to national provisions.

If participation in the study is stopped earlier than the 104 weeks indicated, the participant will be required to attend a modified schedule of visits. The participant will visit the study centre 4 weeks after they stop taking the study drug.

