4.4 Risk Assessment and Guidance for Investigators

Prolongation of the QT interval can occur in patients on probucol. Clinical trials by Yamashita¹⁰ and Kang¹¹ reported significantly more prolonged QT interval adverse events in individuals taking probucol (LorelcoTM), compared to controls. While drug-induced prolonged QT interval can be associated with significant adverse side effects such as ventricular arrhythmia (torsades de pointes), studies involving the use of 500 mg of Probucol daily, reported probucol-induced prolonged QT interval was not associated with, or increased the incidence of, ventricular arrhythmias. Furthermore, Walldius¹² reported that there was no significant difference in cardiovascular clinical events between individuals taking probucol and controls. No malignant arrhythmias or torsades de pointes were reported for either group. The absence of arrhythmias may be due to strict prolonged QT/QTc interval exclusion

Protocol Version 4, 06 OCT 2021

Confidential

Page 19 of 70

criteria. While there is no consensus on upper limit corrected QT/QTc interval values, many studies adopt an absolute QT/QTc interval prolongation of > 500ms. This reduces the risk of ventricular arrhythmia, as participants are discontinued prior to prolonged QT intervals associated with arrhythmia.

While QT prolongation by probucol may not enhance the occurrence of lethal ventricular arrhythmias, studies have identified several clinical risk factors for drug-induced arrhythmias, including probucol. These include;

- Cardiac factors (including congenital long QT syndrome, family history of sudden cardiac death, bradycardia)
- Myocardial hypertrophy
- Heart failure
- Liver disease
- Thyroid Dysfunction
- Renal or hepatic impairment

The above clinical risk factors should be considered prior to treatment with probucol¹³.

Further information regarding Lorelco $^{\text{TM}}$ is available in the Investigator's Brochure.

Protocol Version 4, 06 OCT 2021

Confidential

Page 20 of 70

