6.9 Study Partner Withdrawal

In the event that a study partner withdraws from the study, the study partner will be asked to complete the Study Partner Withdrawal Form and provide a reason for discontinuation. If a study partner withdraws from the study, the participant (or previous study partner) will be asked to nominate a replacement study partner. If a replacement study partner cannot be identified the subject will complete all end of study assessments as deemed appropriate by the Investigator.

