11.6.2 Primary Cognitive Assessment

Alzheimer's Disease Assessment Scales-Cognitive Subscale test (ADAS-Cog)¹⁷: The Alzheimer's Disease Assessment Scale-Cognitive Subscale test (ADAS-Cog) is the most widely used test to measure cognition in RCT's for AD. Taking 30 to 40 minutes to administer it is commonly used in clinical trials as it can determine incremental improvements, or decline

Protocol Version 4, 06 OCT 2021

Confidential

Page 39 of 70

in cognitive functioning. The ADAS-Cog12 version consists of the following tasks: Word Recall Task; Following Commands; Constructional Praxis; Delayed Word Recall; Naming Objects and Fingers; Ideational Praxis; Orientation; Word Recognition; Spoken Language; Comprehension and Word Finding Difficulty. Inclusion of the delayed word recall component has shown an increased ability to detect change in the MCI population. Sensitivity of ADAS-Cog is indicated by a scoring differential of approximately six-fold in patients with the earliest manifestation of AD compared to aged-matched health controls. The full suite of ADAS-Cog will be at baseline, 26, 52, 78 and 104 weeks.

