13.6 Efficacy Analyses

The primary analysis was an intention-to-treat analysis of all randomized participants. Data will be analysed using both Generalised Estimating Equations (GEE) and Bayesian Analysis. The analysis of primary endpoints will use linear mixed-effects models, with random slopes and intercepts.

The Alzheimer's Disease Assessment Scale's cognitive subscale (ADAS-Cog) is the standard primary cognitive outcome measure for evaluating treatments in clinical trials of mild-to-moderate AD. But the utility of ADAS-Cog is compromised primarily due to some of its items suffering from either floor or ceiling effects in different stages of AD. The current scoring methodology is also sensitive to missing item responses, scoring errors and variability in the administration of the ADAS-Cog, which are common in clinical trials.

The scoring methodology ADAS-Cog as proposed by Verma et al. will be utilised as it significantly improves the sensitivity of the ADAS-Cog in measuring progression of cognitive impairment in clinical trials focused in the mild-to-moderate AD stage²¹. This scoring methodology also provides a boost to the efficiency of clinical trials requiring fewer patients and shorter durations for investigating disease-modifying treatments. For patients with missing responses to certain items, this new scoring methodology does not require data imputation and estimates cognitive impairment using the set of items answered by the patients.

Analysis of all primary and secondary endpoints contrasting Probucol and placebo, after adjusting for covariates, will use mixed effects-regression with 'random' intercepts and slopes (as has been used for power calculations). Mean differences and associated 95% confidence intervals will be presented for the 'fixed' effect of Probucol treatment.

Further analysis investigating the relationship between change scores (post-minus pre-intervention scores) for the primary ADAS-Cog with MRI volumes (total GM, hippocampus, and medial temporal lobe volumes) and specific blood biomarkers (eg: plasma lipoprotein-Aβ) will be considered using Pearson (or Spearman where appropriate) correlation analysis. For all other correlations between recorded variables that lack an a priori hypothesis, control of statistical errors will be carried out using Holm-Sidak corrections for multiple comparisons.

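### The protocol names no ADAS-Cog assessment after study drug is stopped, which leaves the intention-to-treat comparison open to bias if stopping is related to drug and outcome

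*Protocol*

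**What the plan says.** **After drug is stopped.** Protocol section 6.8 states: "If participation in the study is stopped earlier than the 104 weeks indicated, the participant will be required to attend a modified schedule of visits". For that schedule it gives only this content: "The participant will visit the study centre 4 weeks after they stop taking the study drug". Section 6.3 agrees. Apart from following adverse events to resolution or stabilisation, it says: "Otherwise, patients will have a final follow-up visit approximately 4 weeks after the last dose of study therapy". Section 6.7 gives the visit's purpose: "Participants will have a safety evaluation 4 weeks following study drug discontinuation".

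**Primary outcome.** Section 11.6.2 sets the times: "The full suite of ADAS-Cog will be at baseline, 26, 52, 78 and 104 weeks". The schedule in Appendix 1 (section 21.1) has no ADAS-Cog mark at the Week 108 follow-up visit.

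**Imaging.** Section 6.1 has PET and MRI done at the last study visit of anyone who discontinues. No matching rule exists for ADAS-Cog.

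**Loss of the study partner.** Section 6.9 says: "If a replacement study partner cannot be identified the subject will complete all end of study assessments as deemed appropriate by the Investigator".

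**Analysis.** Section 13.6 says: "The primary analysis was an intention-to-treat analysis of all randomized participants". The model has random intercepts and slopes, and section 13 rules out imputation. Section 13.2, by contrast, assigns all efficacy analyses to an efficacy-evaluable set.

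**Who stops.** Section 6.7 lists a QTc above 500 ms, or more than 50 ms over baseline, among the criteria for discontinuing. Section 4.4 notes that earlier trials "reported significantly more prolonged QT interval adverse events in individuals taking probucol" than in controls.

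**The concern.** An intention-to-treat analysis needs outcomes on randomised participants whether or not they stay on drug. Here, stopping drug and leaving the study are run together. Section 6.2 mixes reasons for ending therapy with reasons for ending participation, and section 6.7 speaks of reinstating someone in the study after discontinuation. Nothing keeps a willing participant who is off drug on the ADAS-Cog schedule.

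The mixed model then fills the gap by assumption: it projects each stopper's course from the scores before stopping, as if treatment had continued. If benefit fades or stops accruing off drug, that is a different quantity from the effect in all randomised participants. If stopping on one arm also goes with a faster or slower underlying decline, the comparison can be biased even when the drug does nothing. Unequal stopping is foreseeable from the protocol's own text, because a known drug effect is a stopping criterion.

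The collection of imaging from discontinuers shows that their data were thought about for secondary outcomes. The primary outcome was left out.

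**Working it through.** **1. The plan's own figure.** Section 13.1 gives 125 per arm and 20% attrition. 125 / (1 − 0.20) = 156.25, rounded up to 157 per arm, and 2 × 157 = 314. The stated 314 reproduces.

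**2. How many are affected.** 314 × 0.20 = 62.8, about 63 (about 31 per arm). This is an upper figure, because it treats all attrition as permanent stopping of drug before Week 104.
- If stopping times are spread evenly over two years (assumption), the share stopping before Week 26 is 26/104 = 0.25. Then 62.8 × 0.25 = 15.7, about 16 participants (5% of 314), have a baseline score only. About 47 have at least one later score.
- The baseline-only number runs from 0 (all stop after Week 26) to 63 (all stop before it).

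**3. Simple size of the gap.** The planned effect is 25% of a 1.10-unit decline: 0.25 × 1.10 = 0.275. Suppose 20% of the probucol arm stop and retain a share r of the two-year benefit (assumption). The all-randomised effect is 0.275 × (0.80 + 0.20r).
- r = 0: 0.275 × 0.80 = 0.220, and 0.275 / 0.220 = 1.25.
- r = 0.5: 0.275 × 0.90 = 0.2475, and 0.275 / 0.2475 = 1.11.

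The value r = 0 is extreme, since it erases all benefit even for someone who stops near the end. The value r = 0.5 corresponds to even stopping times with benefit that ceases to accrue.

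**4. Simulation.** There were 157 per arm with ADAS-Cog at 0, 26, 52, 78 and 104 weeks, and 400 runs per scenario. A random intercept and slope model was fitted with known covariance. Assumed inputs were residual SD 0.4, intercept SD 1.0, stopping times uniform over two years and no further benefit after stopping. The SD of two-year change was set to the protocol's 0.83. Each cell shows the estimated benefit with scores kept only up to stopping, then with all scheduled scores collected. Monte Carlo error is about 0.10 / √400 = 0.005.

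| Stopping, active/placebo | Unrelated to outcome, true effect 0.275 | Linked to faster decline on active, true effect 0 |
|---|---|---|
| 20% / 20% | 0.274 / 0.248 | 0.097 / 0.002 |
| 25% / 15% | 0.266 / 0.234 | 0.109 / −0.002 |
| 30% / 10% | 0.275 / 0.235 | 0.136 / 0.005 |

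- Stopping unrelated to outcome, no true effect: every estimate lay within 0.006 of zero, even with unequal stopping. There is no bias in that case.
- Stopping unrelated to outcome, true effect 0.275: the ratios are 0.274/0.248 = 1.10, 0.266/0.234 = 1.14 and 0.275/0.235 = 1.17.
- Stopping linked to faster decline on active, no true effect: the spurious benefit is 0.097/0.275 = 35% to 0.136/0.275 = 49% of the planned effect. It disappears when scores after stopping are collected. By symmetry, a link to slower decline would reverse the sign.

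Steps 3 and 4 together give an overstatement of roughly 10% to 25% where benefit is lost after stopping. The linked scenario shows only that a larger error is possible. The documents give nothing with which to set the strength of such a link.

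**The case against.** The strongest case on the other side has five parts.

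- **Stoppers do have data.** A reader might infer that discontinuers contribute no outcome at all. The documents do not support that. Section 6.8 keeps data collected before withdrawal, and the mixed model can use them. The rule against imputation does not exclude partial records. This stands: only those who stop before Week 26 lack a post-baseline score.
- **The text is incomplete rather than explicit.** The altered visit schedule in section 6.8 is otherwise undefined, so a single visit is the natural reading and not a stated rule. The Appendix 1 legend defines an early-termination abbreviation, so a column label may have been lost when the table was read; no weight is put on its absence. Section 6.9 may include a final ADAS-Cog among its end-of-study assessments, at the investigator's judgement. Reinstatement after four weeks is possible. All of this stands, and it is why the point is put as no assessment being named.
- **Bias is not shown.** It is tempting to say that missing data will differ by arm and bias the result. The protocol gives no QT stopping rate and no link between QT events and cognition. The QTc thresholds in section 6.7 are permissive, and section 12.8 treats them as matters for consideration. This stands: bias is a foreseeable risk.
- **Attrition is not all drug stopping.** Some of it will be withdrawal of consent, after which section 6.8 bars further collection. The fix cannot reach those participants. This stands.
- **It belongs in the SAP, and the aim is only preliminary efficacy.** The target quantity and the handling of missing data can be set in the SAP, including the conflict between sections 13.2 and 13.6. Whether scores are collected cannot: a later analysis plan cannot recover visits that never took place. This part fails.

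**Conclusion.** The point holds as a gap in data collection for the primary outcome. Sections 6.3, 6.7 and 6.8 name only a safety visit four weeks after drug is stopped, and no ADAS-Cog is named after that stop. Participants who are not reinstated therefore lack later scores, including Week 104, while section 13.6 claims a comparison of all randomised participants.

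Up to about 63 of 314 are affected if all planned attrition is drug stopping, and fewer to the extent that it is consent withdrawal. About 16 would have no post-baseline score if stopping times are even. The all-randomised effect could be overstated by roughly 10% to 25%. That range rests on assumed stopping rates, retained benefit and variance components, so it indicates direction and rough size only.

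The documents do not support the stronger readings that stoppers have no outcome data or that the comparison is certain to be biased.

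**What to change.** In sections 6.2, 6.8 and 6.9:

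- Separate stopping study drug from withdrawing consent.
- Keep every consenting participant on the existing ADAS-Cog schedule (Weeks 26, 52, 78 and 104) whatever their drug status. Do the same for ADCS-MCI-ADL24 at its scheduled visits (Weeks 26 and 104 in Appendix 1) where a partner is available.
- State that loss of a study partner does not by itself end ADAS-Cog follow-up.
- Spell out the altered visit schedule in section 6.8 and make Appendix 1 agree with it.

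The cost is an amendment with matching consent wording, and continued visits for participants who are off drug. The assessments and visit times already exist, and no dosing or stopping rule changes. The amendment needs to take effect while participants are still in follow-up, because missed scores cannot be recovered later.
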